2.8 Safety analyses

All safety analyses will be based on the safety set.

2.8.1 Adverse events (AEs)

An overview summary of AEs, including counts and percentages of subjects with any AE, AEs related to study treatment, AEs leading to permanent discontinuation of study treatment, AEs leading to dose reductions, AEs leading to dose interruptions, AEs requiring additional therapy, SAEs, SAEs related to study treatment, fatal SAEs, and fatal SAEs related to study treatment will be produced.

A summary of non-serious AEs that occurred in strictly 5% of the subjects or above will be provided (no rounding for the percentage will be used in terms of 5% threshold, e.g. event with 4.9% incidence rate should not be included in this table). The summary will be displayed by SOC and PT. (for clinicaltrials.gov purpose)

AEs will be graded according to the CTCAE v4.0. Adverse events will be coded to the preferred term (PT) level using the Medical Dictionary for Regulatory Activities (MedDRA dictionary) (MedDRA 23.0).

A summary of number and percentage of subjects with any AE by maximum grade will be produced. AEs will be sorted by Preferred term (PT) in descending order of incidence. The summary will use the following algorithms for counting the subject:

- **Preferred term row:** Subjects experiencing the same AE preferred term several times with different grades will only be counted once with the maximum grade.
- **Any event row:** Each subject with at least one adverse event will be counted only once at the maximum grade no matter how many events they have.

In addition, the number and percentage of AEs (all grades) will be summarized and displayed in two ways: 1) in descending order of incidence by PT only and 2) in descending order of

incidence by System Organ Classes (SOC) and PT. In the SOC row, the number of subjects with multiple events under the same system organ class will be counted once.

A separate summary will be provided for study treatment-related AEs. A study treatment-related AE is defined as an AE for which the investigator classifies the relationship to study treatment as “Yes”. A worst case scenario approach will be taken to handle missing relatedness data, i.e. the summary table will include events with the relationship to study treatment as ‘Yes’ or missing. The summary table will be displayed in descending order of incidence by PT only.

All AEs will be listed. Additionally, a listing of subject IDs for each individual AE will be produced.

All SAEs will be tabulated based on the number and percentage of subjects who experienced the event. A summary will also be provided for study treatment-related SAEs. The summary tables will be displayed in descending order of incidence by PT only.

A study treatment-related SAE is defined as an SAE for which the investigator classifies the relationship to study treatment as “Yes”. A worst case scenario approach will be taken to handle missing data, i.e. the summary table will include events with the relationship to study treatment as ‘Yes’ or missing.

SAEs are included in the listing of all adverse events. Separate supportive listings with subject-level details will be generated for all SAEs and Fatal SAEs.

AE summaries will include all AEs occurring during on-treatment period. All AEs collected in the AE (e)CRF page will be listed along with the information collected on those AEs e.g. AE relationship to study drug, AE outcome etc. AEs with start date outside of on-treatment period will be flagged in the listings.

AEs will be summarized by number and percentage of subjects having at least one AE, having at least one AE in each primary system organ class (SOC) and for each preferred term (PT) using MedDRA coding. A subject with multiple occurrences of an AE will be counted only once in the respective AE category. A subject with multiple CTCAE grades for the same preferred term will be summarized under the maximum CTCAE grade recorded for the event. AE with missing CTCAE grade will be included in the ‘All grades’ column of the summary tables.

In AE summaries, the primary system organ class will be presented alphabetically and the preferred terms will be sorted within primary SOC in descending frequency. The sort order for the preferred term will be based on their frequency.

The number of deaths resulting from SAEs suspected to be related to study treatment and SAEs irrespective of study treatment relationship will be provided by SOC and PT.

If the same subject has more than one AE (irrespective of study treatment causality, seriousness and severity) with the same SOC and PT:

- a single occurrence will be counted if there is ≤ 1 day gap between the end date of the preceding AE and the start date of the consecutive AE
- more than one occurrence will be counted if there is > 1 day gap between the end date of the preceding AE and the start date of the consecutive AE

For legal requirements of clinicaltrials.gov (there is no requirement for EudraCT), the following two tables will be provided by system organ class and preferred term on the safety set population:

- On-treatment adverse events which are not SAEs with an incidence greater than and equal to 5%
- On-treatment deaths and SAEs suspected to be related to study treatment

2.8.1.1 Adverse events of special interest / grouping of AEs

An adverse event of special interest is a grouping of adverse events that are of scientific and medical concern specific to dabrafenib and trametinib. These groupings are defined using MedDRA terms, SMQs (standardized MedDRA queries), HGLTs (high level group terms), HLT (high level terms) and PTs (preferred terms). Customized SMQs (Novartis MedDRA queries, NMQ) may also be used. A NMQ is a customized group of search terms which defines a medical concept for which there is no official SMQ available or the available SMQ does not completely fit the need. It may include a combination of single terms and/or an existing SMQ, narrow or broad.

A comprehensive list of MedDRA terms based on clinical review will be used to identify each type of events.

All AE groupings for a clinical program are stored in the Compound Case Retrieval Strategy sheet (CRS) with clear versioning and reference to the MedDRA version used.

The events of special interest will be analysed using the most updated asset specific AESI (Adverse Event of Special Interest) at the time of analysis.

For each specified AESI, number and percentage of subjects with at least one event of the AESI occurring during on treatment period will be summarized.

Summaries of these AESIs will be provided, (specifying grade, SAE, relationship, leading to treatment discontinuation, leading to dose adjustment/interruption, hospitalization, death, etc.). If sufficient number of events occurred, analysis of time to first occurrence will be applied.

A listing of all grouping levels down to the MedDRA preferred terms used to define each AESI will be generated.

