9. A complete physical examination will be performed at Screening and treatment discontinuation; brief physical examinations will be performed at all other time points as indicated. Pelvic and rectal exams will be performed at screening and treatment discontinuation and periodically during treatment as clinically indicated; they do not need to be repeated at screening if they had been performed within 24 weeks of enrollment. Refer to Section 7.3.14 for details.
10. A full skin exam will be done every 8 weeks. Photographic images are required to assess hyperproliferative skin diseases. Upon study treatment discontinuation, a final skin exam is required within 8 weeks of the last dose of study treatment.
11. An ophthalmic examination will be performed at Screening and week 4; after week 4, additional ophthalmic examinations will be performed only as symptomatically warranted. Refer to Section 7.3.12 for details.
12. Refer to Section 7.3.13 for details regarding vital sign measurements.
13. Adverse events will be recorded from the time the first dose of study treatment is administered until 30 days after discontinuation of study treatment. Serious adverse events will be collected over the same time period as AEs except SAEs assessed as **related** to study participation (e.g., protocol-mandated procedures, invasive tests, or change in existing therapy), or study treatment which must be recorded from the time a subject consents to participate in the study up to and including any follow-up contact.
14. All medications the subject takes during the study from the time of screening until 30 days after the last dose of study treatment will be recorded; any new anti-cancer therapy, if taken after study treatment discontinuation will be recorded as detailed in footnote 27.
15. At each time point listed, a single 12-lead ECG will be performed by qualified site personnel after the subject has rested in a semi-recumbent or supine position for at least 5 minutes. Two copies of the ECG tracing should be obtained at the time of the ECG; the first copy will be kept in the subject's medical chart and the second copy will be kept in the study file for retrospective collection by the Sponsor if necessary.
16. See Section 5.8.3.1 for LVEF guidelines for study drug management and requirements for ECHO scans.

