7.3.8 Time Period and Frequency of Detecting AEs and SAEs

The investigator or site staff is responsible for detecting, documenting and reporting events that meet the definition of an AE or SAE.

Adverse events (AEs) will be collected from the time the first dose of study treatment is administered until 30 days after discontinuation of study treatment regardless of initiation of a new anti-cancer therapy or transfer to hospice. In China, SAEs will be recorded from the time the consent form is signed. For all other countries, SAEs will be collected over the same time period as stated above for AEs. However, any SAEs assessed **as related** to study participation (e.g., study treatment, protocol-mandated procedures, invasive tests, or change in existing therapy), will be recorded from the time a subject consents to participate in the study up to and including any follow up contact. All SAEs will be reported to Novartis within 24 hours, as indicated in Section 7.3.10.

After discontinuation of study treatment, the investigator will monitor all AEs/SAEs that are ongoing until resolution or stabilization of the event or until the subject is lost to follow-up. At any time after 30 days the investigator may report any adverse event that they believe possibly related to study treatment.

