7.3.14.1 Dermatological Exams

A full skin exam is required at screening and every 8 weeks to assess cutaneous malignancies and proliferative skin diseases. Upon study treatment discontinuation, a final skin exam is required within 8 weeks of the last dose of study treatment. Medical photographs should be taken for patients with such skin abnormalities.

Dermatologic skin exams may be referred to a dermatologist, if needed. If possible, the same physician should perform each examination for the duration of the study to ensure consistency between evaluations.

[figure not shown]

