9.3.5.2.2 Adverse Events

Adverse events will be coded using the standard MedDRA and grouped by system organ class. Adverse events (AEs) will be graded by the investigator according to the NCI CTCAE, version 4.0.

Events will be summarized by frequency and proportion of subjects, by system organ class and preferred term. Separate summaries will be given for all AEs, drug-related AEs, SAEs, and AEs leading to treatment discontinuation.

If the AE is listed in the NCI CTCAE table, the maximum grade will be summarized.

Any AEs of special interest (including SCC and other proliferative diseases) will be summarized as detailed in the SAP.

The incidence of death and the primary cause of death will be summarized.

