2.1.3.6 On-treatment assessment/event and observation periods

For adverse event reporting the overall observation period will be divided into three mutually exclusive segments:

1. **pre-treatment period:** from day of subject's informed consent to the day before first administration of study treatment
2. **on-treatment period:** from date of first administration of study treatment to 30 days after date of last actual administration of any study treatment (including start and stop date)
3. **post-treatment period:** starting at day 31 after last administration of study treatment.

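### The final skin exam may come up to 8 weeks after the last dose, but the SAP's special-interest table stops at 30 days, so a skin malignancy dated to days 31–56 is not counted there

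*SAP*

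**What the plan says.** **Detection.** Protocol 7.3.14.1 states: "A full skin exam is required at screening and every 8 weeks to assess cutaneous malignancies and proliferative skin diseases". Both that section and Table 20, footnote 10, add: "Upon study treatment discontinuation, a final skin exam is required within 8 weeks of the last dose of study treatment". Protocol 9.3.5.2.2 makes these findings events of special interest (AESIs): "Any AEs of special interest (including SCC and other proliferative diseases) will be summarized as detailed in the SAP". cuSCC is always reportable as an SAE (5.8.4.4), and so are new primary cancers other than basal cell carcinoma (7.3.2.2 g).

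**Counting.** The SAP's on-treatment period runs "from date of first administration of study treatment to 30 days after date of last actual administration of any study treatment" (2.1.3.6), and the post-treatment period starts on day 31. SAP 2.8.1 says "AE summaries will include all AEs occurring during on-treatment period", with events that start outside the period flagged in listings. For AESIs, SAP 2.8.1.1 says the "number and percentage of subjects with at least one event of the AESI occurring during on treatment period will be summarized".

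**Collection.** Protocol 7.3.8 collects AEs "until 30 days after discontinuation of study treatment regardless of initiation of a new anti-cancer therapy". Beyond that, SAEs judged related are recorded through any follow-up contact, and the investigator may report other possibly related events.

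**The concern.** The exam that closes surveillance for drug-related skin cancer has an outer limit 26 days later than the table that reports it. Scheduled exams are 8 weeks apart, so a lesion that arose on treatment can first be seen, and given its start date, after day 30 in a subject who followed the protocol throughout. Such an event drops out of the count by rule.

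The events matter to the plan. Fewer hyperproliferative skin lesions is part of the protocol's rationale for combining the two drugs (Protocol Summary, 1.2, 1.4.2), and safety is a secondary objective. Few cases are expected in about 65 subjects, so a single omission is visible, and an omission can only lower the reported rate.

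**Working it through.** The plan states no figure to reproduce, so the check compares windows, follows a late event through the rules, and then looks at scale.

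**1. Windows**
- Latest final skin exam: 8 × 7 = 56 days after the last dose (Protocol 7.3.14.1; Table 20, footnote 10).
- End of AESI counting: day 30 (SAP 2.1.3.6, 2.8.1.1).
- Uncovered: days 31–56, that is 56 − 30 = 26 days, or 26/56 = 46% of the exam allowance. This is a share of calendar days, not of exams or events.

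**2. What happens to an event dated to day 45**
- *cuSCC judged related:* collected under Protocol 7.3.8. It is not in the AESI table, nor in the registry table of related SAEs, which SAP 2.8.1 labels on-treatment. It appears in listings with a flag.
- *New primary melanoma judged unrelated:* 7.3.8 has stopped collecting it, while 7.3.3 requires any new primary cancer to be reported as an SAE and sets no causality condition. Whether it reaches the database depends on which section the site follows.
- *Non-serious proliferative lesion:* AE collection ended at day 30, so it is recorded only if the investigator thinks it possibly related and chooses to report it.
- *General SAE table:* SAP 2.8.1 says all SAEs are tabulated and gives no window in that sentence. A later sentence in the same section limits AE summaries to the on-treatment period. The text does not settle which rule applies.

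**3. Precedent in the SAP.** Section 2.8.2 classifies deaths as ≤30 or >30 days from the last dose and produces both on-treatment and all-death summaries. Nothing equivalent is specified for malignancies.

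**4. What narrows the gap**
- Table 20 marks a dermatological exam and a complete physical exam at the discontinuation visit. Protocol 7.3.14 includes a full skin exam in the complete physical, and footnote 27 puts that visit within 30 days of the last dose.
- Footnote 27 also lets an assessment from the preceding 30 days stand in for one at that visit, and footnote 10 keeps its 8-week limit. A first sighting on days 31–56 therefore needs the discontinuation exam to be waived, missed or negative, and a later exam to be done.
- Counting follows the recorded start date. A lesion examined on day 50 but dated to day 25 is counted.

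**5. Scale (illustration)**
- One subject of 65: 1/65 = 1.5 percentage points.
- The protocol's own combination rates (1.2.3) are 1% (including keratoacanthoma), 2% and 7%. Expected subjects over the whole study: 65 × 0.01 = 0.65; 65 × 0.02 = 1.3; 65 × 0.07 = 4.55.
- If there were two cases and one was left out, 2/65 = 3.1% (exact 95% CI 0.4 to 10.7) would be reported as 1/65 = 1.5% (0.0 to 8.3).
- Number of cases in the gap: not given. As an assumption, let treatment last about as long as the cited median PFS of 9.3 to 11.4 months, and let every exam be equally likely to find a case. With the SAP's 30.4375-day month, 9.3 × 30.4375 / 56 = 5.1 and 11.4 × 30.4375 / 56 = 6.2 eight-weekly exams come before the final one, which is then about 1 in 6 or 7. If every final exam fell after day 30, it would find about 0.65/7 = 0.1 to 4.55/6 = 0.8 cases. With discontinuation exams done within 30 days, the number is smaller.

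**The case against.** The best reply is that the plan already closes most of the gap. A full skin exam is due within 30 days of stopping, so the 8-week limit is a fallback. Late related events are not hidden: they are listed, and with so few cases in a single-arm trial a subject-level listing shows each one. The 30-day window also matches the protocol's AE collection period. The counting windows behind the cited 1% to 7% rates are not in the documents, so a 56-day headline rate could be less comparable with them.

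Much of this stands. It limits the size of the problem and is a good reason to keep the 30-day tables as they are. It does not explain why a named AESI has a detection allowance that its only specified count cannot reach, when deaths get an all-time summary.

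Two stronger inferences are tempting and are not supported:
- *Late cases vanish from every safety table.* The sentence on the SAE table has no window, so that table's content is ambiguous, and collected events remain in the listings.
- *Nearly half of the cases, or of the incidence, is lost.* The 46% counts calendar days. The expected 0.65 to 4.55 cases cover the whole study, not days 31–56.

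**Conclusion.** The mismatch is real and limited. The AESI table omits any skin malignancy or proliferative lesion with a recorded start on days 31–56, although the protocol allows the final exam for exactly these conditions in that interval. The effect is in one direction, and each affected subject lowers the reported incidence by about 1.5 percentage points. How many are affected cannot be derived from the documents; under the assumptions shown, it is below one case.

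The conclusion rests on three conditions: some final exams use the allowance beyond day 30, a lesion found there is dated to the exam or at least after day 30, and it is recorded at all. A reader might also infer that the reported rate would be biased low against the cited trials. That does not follow, because their counting windows are not given.

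This is a cheap improvement to the SAP. It does not threaten the trial's safety conclusions.

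**What to change.** Keep the 30-day AE and AESI tables unchanged, and make these changes to the SAP:
- **2.8.1.1:** for cuSCC, treatment-emergent malignancy and proliferative skin disease, add a row counting subjects with an event from first dose through the final skin exam (last dose + 56 days), regardless of causality. Show days 31–56 separately and flag events that start after new anti-cancer therapy. This follows the ≤30 / >30 day split already used for deaths in 2.8.2.
- **2.8.1:** state which window governs the table of all SAEs.
- **Footnote to the new row:** late events not judged related may be under-collected, because Protocol 7.3.8 and 7.3.3 are not reconciled on new primary cancers. Late non-serious lesions may also be missing.

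Changing collection under Protocol 7.3.8 would recover nothing for this trial: the SAP gives the last visit as 19-Apr-2021 (2.1.1). The new row also stays subject to the 30-Jun-2019 cut-off for Mainland Chinese patients in the same section.

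The cost is a few lines of SAP wording, one extra row per affected table, and possibly a slightly higher reported rate. It uses only data already collected.

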2.8.2 Deaths

In the event that a subject has withdrawn consent, no data after the withdrawal of consent date from this subject including death is supposed to appear in the database, which should be part of the data cleaning process.

All deaths occurring any time from the time of informed consent to the clinical cut-off date will be summarized based on the number and percentage of subjects. This summary will classify subjects by time of death relative to the last dose of medication (> 30 days or ≤ 30 days) and primary cause of death (disease under study, SAE related to study treatment, or other). A supportive listing will be generated to provide subject-specific details on subjects who died.

Separate summaries for on-treatment and all deaths (including post-treatment death) will be produced by system organ class and preferred term.

All deaths and deaths prior to starting treatment will be listed.

2.8.3 Laboratory data

The assessment of laboratory toxicities will examine the following laboratory tests:

Hematology: Hemoglobin (HGB), White Blood Cell (WBC) count, Total Neutrophils, Lymphocyte, Monocyte, Basophil and Eosinophil counts, and Platelet count. Basophils, Eosinophils and Monocytes are not gradable by CTCAE v4.0.

Clinical Chemistry: Sodium, Potassium, Calcium, Glucose, Blood Urea Nitrogen (BUN), Creatinine, Estimated Creatinine Clearance, Albumin, Lactate Dehydrogenase (LDH), and phosphate. BUN, LDH and Estimated Creatinine Clearance are not gradable by CTCAE v4.0. For Sodium, Potassium, Calcium, Phosphate, Lymphocyte and Glucose two bi-directional parameters (hyper and hypo), the tests will be graded by CTCAE v4.0 in both directions.

Liver Function Tests: Aspartate amino transferase (AST), Alanine amino transferase (ALT), Alkaline phosphatase, Total bilirubin (total) and Direct bilirubin. All these tests are gradable by CTCAE v4.0.

Coagulation Tests: Prothrombin time (PT) or International Normalized Ratio (INR), and partial thromboplastin time (PTT). These tests are collected only at baseline. Therefore these tests will not appear in any summaries of changes from baseline.

Summaries of worst case grade increase from baseline grade will be provided for all the lab tests that are gradable by CTCAE v4.0. These summaries will display the number and percentage of subjects with a maximum on-therapy grade increasing from their baseline grade. Any increase in grade from baseline will be summarized along with any increase to a maximum grade of 3 and any increase to a maximum grade of 4. Missing baseline grade will be assumed as grade 0. In addition, the summary will include grade increase from baseline by scheduled visits. For laboratory tests that are graded for both low and high values, summaries will be done separately and labeled by direction, e.g., sodium will be summarized as hyponatremia and hypernatremia.

For lab tests that are not gradable by CTCAE v4.0, summaries of worst case changes from baseline with respect to normal range will be generated. Decreases to low, changes to normal or no changes from baseline, and increases to high will be summarized at each scheduled visit as well as for the worst case post baseline. If a subject has a decrease to low and an increase to high during the same time interval, then the subject is counted in both the “Decrease to Low” categories and the “Increase to High” categories. Flag the earliest worst-case normal range values per time point. The worst-case for normal range values is bi-directional (either High or Low or both). If subject has both High and Low values in same time point, then flag both the earliest High record and the earliest Low record. If subject does not have a High or a Low value during the time point, then flag the subject's earliest in-range value. For visit timepoints: Baseline records are always flagged. Pre-therapy records, imputed records, and unscheduled records are not eligible for flagging.

Separate summary tables for (hematology, chemistry and liver function) laboratory tests will be produced.

Unless otherwise specified, the denominator in percentage calculation at each scheduled visit will be based on the number of subjects with non-missing value at each particular visit. For

subjects with a history of chronic Hepatitis B and/or Hepatitis C, the following tests will be performed at Screening:

- Viral hepatitis serology (HBs Antigen, HBc Antibody, HBs Antibody, HCV Antibody);
- Hepatitis BDNA; and/or
- Hepatitis C RNA.

As it is anticipated that the number of subjects with a history of chronic Hepatitis B and/or Hepatitis C will be small these data will only be listed and not summarized.

Summaries of hepatobiliary laboratory events including possible hy's law cases will be provided in addition to what has been described above.

On analyzing laboratory, data from all sources central and local laboratories will be combined. The summaries will include all assessments available for the lab parameter collected no later than 30 days after the last study treatment administration date.

The following summaries will be produced for hematology and biochemistry laboratory data (by laboratory parameter):

- Worst post-baseline CTC grade (regardless of the baseline status). Each subject will be counted only for the worst grade observed post-baseline.
- Shift tables using CTC grades to compare baseline to the worst on-treatment value
- For laboratory tests where CTC grades are not defined, shift tables using the low/normal/high/(low and high) classification to compare baseline to the worst on-treatment value.

The following listings will be produced for the laboratory data:

- Listings of all laboratory data, with CTC grades and classification relative to the laboratory normal range. Lab data collected during the post-treatment period will be flagged.
- Listing of all CTC grade 3 or 4 laboratory toxicities

Liver function parameters

Liver function parameters of interest are total bilirubin (TBL), ALT, AST and alkaline phosphatase (ALP). The number (%) of subjects with worst post-baseline values as per Novartis Liver Toxicity guidelines will be summarized:

The following summaries will be produced:

- ALT or AST > 3xULN
- ALT or AST > 5xULN
- ALT or AST > 8xULN
- ALT or AST > 10xULN
- ALT or AST > 20xULN
 - TBL > 2xULN
 - TBL > 3xULN
 - ALT or AST > 3xULN & TBL > 2xULN

ALT or AST > 3xULN & TBL > 2xULN & ALP < 2xULN (potential Hy's law)

Potential Hy's Law events are defined as those subjects with concurrent occurrence of AST or ALT > 3xULN and TBL > 2xULN and ALP < 2xULN in the same assessment sample during the on-treatment period. Further medical review has to be conducted to assess potential confounding factor such as, liver metastases, liver function at baseline etc.

